7.5.2.8 Recommendations for Treatment of Diarrhoea

Patients should be made aware of the risk of diarrhoea while receiving treatment with AZD2014. Patients should be advised to drink sufficient fluids and have a supply of loperamide available throughout treatment. However, loperamide should not be administered prophylactically.

As soon as the first liquid stool occurs, patients should start treatment with loperamide immediately and also take electrolyte-containing fluids. Patients should inform their study doctor.

The recommended antidiarrheal treatment is loperamide; to be administered as per package information and usual clinical practice .Loperamide should not be administered for more than 48 consecutive hours.

Hospitalisation is recommended for management of diarrhoea under the following circumstances:

- Diarrhoea associated with fever
- Diarrhoea requiring intravenous hydration
- Diarrhoea persisting beyond 48 hours following the initiation of high-dose loperamide therapy.

Please refer to Section 7.5.1 for dose modifications required for \geq Grade 3 diarrhoea.

7.5.2.9 Recommendations for Evaluation and Treatment of Electrolyte changes

AZD2014, like other mTOR inhibitors inhibits pump mechanisms in renal tubules, leading to hypokalaemia and hypophosphataemia in a small proportion of patients. The presence of biochemical abnormalities should be monitored as per the protocol and electrolyte abnormalities should be corrected using oral supplements. The Investigator should also consider whether other medication the patient may be receiving, such as diuretics may have contributed to these abnormalities.

7.6 Treatment Compliance

Treatment compliance for AZD2014 will be monitored using patient diaries. Patients will be asked to complete patient treatment diaries and return any unused tablets along with the diary at the end of every cycle for reconciliation or upon any dose modification. Staff must note in the patient diary the number of tablets remaining at the end of each cycle.

Accountability for rituximab will be via pharmacy drug accountability logs and the treatment CRF.

7.7 Supportive Treatment

- Pre-medication for rituximab dosing: hydrocortisone 100-200mg IV, antihistamine, and paracetamol are permissive according to local standards
- RBC transfusion is permissive and advised in the event of symptomatic anaemia or a haemoglobin falling below 80 g/L. If anaemia occurs, an assessment of underlying causality should take place and non-IMP related causes considered.
- Platelet transfusion should be used in the following situations: as treatment of a bleeding event with a platelet count < 50 x 10⁹/l, platelets < 20 x 10⁹/l with concomitant infection or platelets < 10 x 10⁹/l in asymptomatic patients
- Grade 4 neutropenia (neutrophil count < 0.5 x 10⁹/l) should always be treated with GCSF according to local policy. Specific G-CSF and regimens should be according to local policy. However, please note the following guidance from the American Society of Clinical Oncology (ASCO) guidelines (2006 update) (65):

GCSFs should be continued until neutrophil count is $\geq 2x10^9$ /l In adults the recommended G-CSF dose is 5 µg/kg/d

 Patients with rapidly proliferating tumour and high tumour burden are at risk of tumour lysis syndrome (TLS). These patients should be monitored closely and managed according to best medical practice. Management of TLS may include aggressive hydration, monitoring of renal function, correction of electrolyte abnormalities, anti-hyperuricaemic therapy, and supportive care. There is no specific indication for rasburicase when AZD2014 is given to treat DLBCL.

7.8 Concomitant Medication

7.8.1 Concomitant treatment with CYP inhibitors, inducers and substrates

If a patient requires short-term administration of a restricted CYP3A4/5, Pgp or BCRP **inhibitor** AZD2014 treatment must be withheld for three days prior to administration and not restarted until the concomitant therapy has been discontinued for the appropriate time period described in Appendix 2.

If a patient requires short-term administration of a restricted CYP3A4/5, Pgp (MDR1) or BCRP isoenzyme **inducer** this should be clearly documented in the Case Report Form (CRF) and may then be permitted, but the Investigator will be informed that this could lead to lower levels of study drug and a potential reduction in clinical efficacy.

If a patient requires short term administration of restricted **substrates** of OATP1B1, OATP1B3, MATE1 or MATE2K AZD2014 treatment must be withheld for 3 days prior to the first administration and not restarted until the concomitant therapy has been discontinued for the appropriate time period *described in Appendix 3*.

Information on all concomitant treatments given during the study with reasons for the treatment should be recorded in the CRF. If medically feasible, patients taking regular medication other than those excluded from this study should be maintained on it throughout the study period.

The lists of CYP inhibitors, inducers and substrates are not exhaustive and the absence of a drug from these lists does not imply that its combination with AZD2014 is safe.

7.8.2 Other Concomitant Treatments

Information on any treatment pertinent to the inclusion/exclusion criteria in the 4 weeks prior to starting study treatment and all concomitant treatments given during the study with reasons for the treatment should be recorded. If medically feasible, patients taking regular medication, with the exception of potent or moderate inhibitors or inducers of CYP3A4/5 or CYP2C8, should be maintained on it throughout the study period.

- Patients who begin warfarin, or other vitamin K antagonists, therapy should be advised to have their anticoagulation monitored more frequently when receiving AZD2014 and should stop medication with AZD2014 at thrombocytopenia CTCAE Grade 3 or higher.
- Patients may continue to receive therapeutic bisphosphonates and erythropoietin preparations (e.g. Procrit, Epogen, Aranesp), if they were receiving them prior to beginning study treatment.
- Blood transfusions are allowed during the study.
- Other medication e.g. anti-emetics that are considered necessary for the patient's safety and well-being may be given at the discretion of the investigators.

Primary prophylaxis with anti-viral, anti-fungals and anti-Pneumocystis carinii pneumonia (*PCP*) medication are not required. These should be used according to local policy; however it should be noted that:

1. The systemic anti-Pneumocystis carinii pneumonia medication dapsone is **contraindicated** due CYP3A4/5 inhibitory effect.

2. Pentamidine **should NOT** be used for this indication due to its cardiac effects

Palliative radiotherapy to a site which does not contain a target lesion is permissible. Concomitant use of any other anticancer therapy, or moderate-to-significant inhibitors of CYP3A4 (Appendix 2), are prohibited.

Concomitant vaccination with live virus vaccines during rituximab treatment and for the duration the patient is peripherally depleted is prohibited.

7.9 Treatment discontinuation and Patient Withdrawal

In the event of discontinuation of study treatment, e.g. unacceptable toxicity or patient choice, full details of the reason/s for discontinuation should be recorded on the appropriate pages on the CRF. All patients, including non-compliant subjects, should be followed up according to the protocol unless they withdraw specific consent.

In the event of a patient's decision to withdraw from the trial, the Investigator should ascertain from which aspects of the trial the patient wishes to withdraw and record the details on the appropriate

CRF. If a patient chooses to withdraw from treatment only, the patient should discontinue treatment and continue to be assessed in accordance with the protocol.

If a patient wishes to withdraw from the trial (i.e. including trial specific assessments), but is willing for further data to be supplied to the Trials Office, then further routine "follow-up" data (e.g. disease status and survival) will continue to be supplied by the Investigator to the Trials Office. All information and blood/tissue samples collected up until point of retraction will be retained and analysed.

Patients who stop treatment due to AEs (clinical or laboratory) will be treated according to accepted medical practice and followed up as per protocol. All pertinent information concerning the outcome of such treatment must be recorded in the CRF.

The following are justifiable reasons for the Investigator to stop study treatment:

- unforeseen events: any event which in the judgement of the Investigator makes further treatment inadvisable
- serious violation of the study protocol (including persistent patient non-attendance and persistent non-compliance)
- stopping by the Investigator for clinical reasons not related to the study drug treatment

Patients must stop study treatment in the event of:

- SAE requiring permanent discontinuation of treatment
- the patient becoming pregnant
- Clinically significant ECG changes
- Interstitial lung disease
- Stevens-Johnson syndrome, Progressive multifocal Leukoencephalopathy or other significant infusion related reactions

If trial treatment is discontinued the patient must attend clinic for the end of treatment visit and 30 days (+/- 5 days) after their last trial treatment for the 30 days post treatment visit, unless they have withdrawn consent for these assessments.

End of treatment visit assessments

- Clinical assessment to include vital signs (heart rate, systolic and diastolic BP, oxygen saturation (pulse oximetry), weight, and temperature
- Constitutional symptoms will include , night sweats and recurrent fever ≥38.0°C,
- Laboratory tests to include full blood counts, Standard biochemistry including glucose, Hba1c, triglycerides and cholsterol⁻
- ECG
- PET-CT to include contrast enhanced CT (if Progression only)
- ECOG
- Con meds
- AEs

30 days post treatment assessments (+/- 5 days)

- Clinical assessment to include vital signs (heart rate, systolic and diastolic BP, oxygen saturation (pulse oximetry), , weight, and temperature
- Laboratory tests to include full blood counts, Standard biochemistry inclusing glucose, Hba1c, triglycerides and cholsterol
- ECOG
- AEs

Following study treatment discontinuation the patient should be treated at the Investigator's discretion.

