1.2.3.2 Overall Safety of AZD2014

AZD2014 is considered to be generally well tolerated with most of the AEs classified as CTCAE grade 1 and 2. AEs have also been shown to resolve quickly after short periods of dose interruptions, which allowed patients to stay on the drug for long periods of time (over 1 year). Fatigue, mucositis, rash, nausea, vomiting, diarrhoea, hyperglycaemia and decreased appetite, risk of pneumonitis and infections were the AEs consistently amongst the most frequently reported overall, and those reported as related to AZD2014 by the Investigators. These AEs were also those reported with the highest severity grade and were those AEs most commonly leading to dose interruption and/or permanent discontinuation of AZD2014. These events were generally reversible within 1 week by cessation of AZD2014. The AE profile of continuous and intermittent dosing schedules varied slightly. Although gastrointestinal events were observed more frequently in the intermittent schedules, there have been no reports of rash or hyperglycaemia so far for the intermittent dosing schedules.

Overall, no clinically significant changes were observed in heart rate or blood pressure (BP). Single intermittent systolic or diastolic BP values above and below normal values were reported in a few patients. Intermittent higher heart rates >100 bpm were observed, and tachycardia in some patients.

No clinically significant changes were observed in vital signs or laboratory data overall. Review of emerging laboratory data did not reveal clinically significant liver function test (LFT) abnormalities considered related to AZD2014. Transaminase increases (ALT or AST) were reported as AEs in some patients; the majority were CTCAE grade 1 and were not considered related to AZD2014 by the reporting investigator. Laboratory data suggest that for most patients who do have reductions in cell counts, values return to patients' baseline on stopping AZD2014. The clinical relevance of these changes appears low given that there was no excess of related AEs such as infection, fungal disease, viral disease, dyspnoea, or bleeding within these patients when compared with patients not noted as having reductions, and there were no events of greater severity. ECG repolarisation changes were seen in some patients. However, there were no associated significant QRS morphology changes and the clinical significance of these changes is unknown.

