7.3.3 ECG

ECGs should be taken on cycle 1 day 1 pre dose and, 2 hrs post dose .If the cycle 1 day 1 ECG taken as part of the monotherapy study is abnormal then ECG measurements should be taken on day 1 of all subsequent cycles. During the combination study ECGs should be taken on cycle 1 day 1 pre dose and, 2 hrs post dose and day 1 of all subsequent cycles unless indicated otherwise.

Twelve-lead ECGs will be obtained after the patient has been resting semi-supine for at least 10 minutes. All ECGs should be recorded with the patient in the same physical position. For each time point 1 ECG recording should be taken.

If an abnormal pre dose ECG finding is considered by the Investigator to be clinically significant, it should be reported as a concurrent condition. During the study, clinically significant abnormal ECG findings not present at pre dose should be reported as an AE. If present, the clinical signs and symptoms associated with the abnormal finding should be reported as the AE with the ECG abnormality given as explanatory information. Further ECGs should be performed until recovery if a significant abnormality is detected (or as clinically indicated)

Troponin (additionally other cardiac markers, i.e. AST/ALT and LDH depending on the investigators decision if clinically indicated) should also be assessed on identification of abnormal ECG findings, e.g. new repolarisation abnormalities. A repeat cardiac marker assessment should also be performed 24 hours later, if such findings occur, the same Troponin isoform should be assessed at each of the visits.

An ECG should be performed at any cardiac event with symptoms that may be due to cardiac ischaemia, or arrhythmia (such as chest pain or palpitations). An ECG will also be captured in all cases of dyspnoea and pulmonary oedema and additionally at the discretion of the investigator if clinically indicated.

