7.5.1 General dose modifications for toxicities

Dose reduction and discontinuation guidelines for haematologic and non-haematologic toxicities due to AZD2014 are shown in Table 2 and 3. Dose re-escalation is not permitted.

Table 2.	Dose modifications and discontinuation criteria for non-haematologic toxicities*

NCI CTCAE Toxicity Grade	Action
Grade 1, or 2	None
Grade 3 or 4 and/or clinically significant	
Expected manageable/reversible with dose reduction	Hold study drug until meets one of the criteria below:
Toxicity remains (despite dose interruption) grade 3 or 4 or is clinically significant > 14 days	Discontinue study drug
Toxicity lasts 14 days or less and resolves to grade 2 or less or is no longer clinically significant	Reduce dose level per Table 1 and restart once toxicity has resolved to grade 2 or less or is no longer clinically significant
Grade 3 or 4 and/or clinically significant	
Not expected to be manageable/reversible with dose reduction	Discontinue study drug
Recurrence of Grade 3	Reduce one more dose level is available (see table 1), or if not discontinue study drug. NB note option of continuous dosing schedule as mentioned in 7.5

 Table 2.
 Dose modifications and discontinuation criteria for non-haematologic toxicities*

NCI CTCAE Toxicity Grade Action	
Recurrence of Grade 3 cardiac event ^a	Discontinue study drug
Recurrence of Grade 4	Discontinue study drug

* If the below specific recommendations for stomatitis/oral mucositis, hyperglycaemia, ILD/pneumonitis, ECG-changes and rash disagree with table 2 please follow the below not recommendations not table 2.

	Table 3.	Dose modifications and discontinuation criteria for haematological toxicitie
--	----------	--

NCI CTCAE toxicity grade	Action
Thrombocytopenia	
Grade 1, 2 or 3 (without bleeding)	None
Grade 3 (with bleeding) or grade 4	Hold study drug until it meets one of the criteria below:
Toxicity remains (despite dose interruption) grade 3 (with on-going bleeding episodes) or 4 > 14 days	Discontinue study drug
Toxicity lasts 14 days or less and resolves to grade 2 or less	Reduce dose level per table 1 and restart once toxicity has resolved to grade 2 or less
Neutropenia (NB GCSF is permitted as per local p	olicy)
Grade 1, 2 or 3	None
Grade 4	Hold study drug until it meets one of the criteria below:
Toxicity remains (despite dose interruption and GCSF) grade 4 > 14 days	Discontinue study drug

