7.5.2.5 Recommendations for Evaluation and Treatment of Interstitial Lung Disease

Should a patient experience any new respiratory symptoms including cough, dypsnoea, lower respiratory tract infections not clearly explained by other factors such as disease progression or anaemia, a high resolution CT scan should be performed. In addition, pulmonary function tests should be performed. The test should include the highest of 3 forced expiratory volumes (FEV1), forced vital capacity (FVC), and carbon monoxide diffusing capacity (DLCO% & DLCO). A recent haemoglobin measurement should be available at DLCO evaluation.

If these investigations are suggestive of pneumonitis or interstitial lung disease and causality with the study drug cannot be excluded, treatment should be interrupted. In more severe cases treatment with corticosteroids should be considered

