7.5.2.6 Recommendations for Evaluation and Management of ECG Changes

Patients who develop persistent, confirmed T wave repolarisation abnormalities (inversion or flattening) on regularly scheduled ECGs may be referred for a cardiology opinion.

ECG monitoring should be continued as per the trial schedule, as well as a troponin measurement (within 24 of the abnormality). ECG, Troponin and LV function assessment should also be conducted at trial discontinuation and 30 days follow-up visit (to document recovery while off drug)

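### Section 7.9 makes clinically significant ECG changes a mandatory stop, Table 2 allows a reduced-dose restart, and no text says which prevails

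*Protocol*

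**What the plan says.** Four places in the protocol bear on a patient who develops an ECG change on AZD2014.

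- **Section 7.9** (treatment discontinuation): "Patients must stop study treatment in the event of" five bullets. One is clinically significant ECG changes and another is interstitial lung disease (ILD). Neither carries a condition on grade, causality, persistence or recovery.
- **Section 7.5.1, Table 2** (non-haematological toxicity): one block of rows covers toxicity that is grade 3 or 4 and/or clinically significant. If it is expected to be manageable with dose reduction, the drug is held. The condition for resuming is "Toxicity lasts 14 days or less and resolves to grade 2 or less or is no longer clinically significant", and the patient then restarts one dose level lower. If it lasts longer, or is not expected to be manageable, the drug is discontinued. A separate row discontinues the drug when a grade 3 cardiac event recurs.
- **Footnote to Table 2**: where the specific recommendations that follow, including those for ECG changes and ILD/pneumonitis, disagree with the table, they are to be followed instead. Section 7.9 is not mentioned.
- **Section 7.5.2.6** (ECG changes): persistent, confirmed T-wave abnormalities may be referred to cardiology, "ECG monitoring should be continued as per the trial schedule", and troponin is measured. No hold or stop is given.

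**The concern.** The same finding, an ECG change judged clinically significant, leads to different treatment decisions depending on which section the investigator opens. Section 7.9 ends treatment. Table 2 can bring the patient back at 100 mg twice daily, the first reduced level in Table 1. Investigators managing a toxicity will naturally turn to the dose-modification tables first.

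What is at stake is re-exposure after a cardiac signal that the discontinuation section treats as disqualifying, and different handling across the sites of a multicentre trial. The situation is foreseeable: section 1.2.3.2 reports ECG repolarisation changes in some patients treated with AZD2014 and says that "the clinical significance of these changes is unknown".

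**Working it through.** No figure in the plan depends on this point, so the check is a comparison of the texts.

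**1. Is the stop in 7.9 permanent?** It stands in the section on discontinuation, beside pregnancy, and that section goes on to require an end-of-treatment visit and a visit 30 days after the last treatment. I read it as permanent.

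**2. Does Table 2 reach the same event?** Yes. Its entry condition includes clinical significance as an alternative to grade, and that is the trigger in 7.9.

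| Clinically significant ECG change, first occurrence | Section 7.9 | Table 2 |
|---|---|---|
| Expected manageable, settles within 14 days | Stop | Hold, then restart one level lower |
| Expected manageable, lasts more than 14 days | Stop | Discontinue |
| Not expected manageable | Stop | Discontinue |

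The two agree in the second and third rows and conflict in the first.

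**3. Does the cardiac row remove the conflict?** No. It acts on recurrence of a grade 3 cardiac event, which presupposes that a patient can have been restarted after a first one.

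**4. Does the footnote remove it?** No. It sends the reader from Table 2 to 7.5.2.6. That section has no treatment action, so either it does not disagree with Table 2 and the restart stands, or it is read as monitoring only and the drug continues. Neither reading produces the stop in 7.9.

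**5. Does any other text rank 7.9 against 7.5?** None was found. By contrast, 7.5.2.3 states permanent discontinuation for Stevens-Johnson syndrome, which matches the 7.9 bullet. Where the dose-modification text carries the stop itself, the two sections agree.

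**6. Reach.** One of the five bullets in 7.9 is contradicted. The rule applies to 30 + 6 = 36 planned patients. The protocol gives no rate for clinically significant ECG changes. An assumed rate would give the chance that such an event occurs, not the chance that a patient is wrongly restarted, so none is used.

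**7. Endpoints.** Section 12.6 counts a toxicity that causes a treatment delay or dose modification in the first 2 cycles as a tolerability failure (at most 5 allowed in 15 patients, 9 in 30). A hold under Table 2 in that window already counts, whether or not the patient restarts.

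**The case against.** The best defence is that the wording already implies a ranking. Section 7.9 is the dedicated discontinuation section and says *must*; the 7.5.2 subsections are headed as recommendations and use *should* or *may*. A cautious investigator would stop. Section 7.5.2.6 also schedules tests at discontinuation and at the 30-day visit to document recovery off drug, which fits a stop. The protocol refers to the Investigator Brochure for more detail on cardiac findings, and that document is not available here. All of this makes the correct action more likely, but none of it states it. Table 2 is itself directive and gives an explicit restart instruction for the same trigger.

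A reader might infer three stronger points that the documents do not support:

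- **That the ILD rules contradict each other.** Section 7.5.2.5 acts earlier, on findings that are only suggestive: if "causality with the study drug cannot be excluded, treatment should be interrupted". It gives no restart rule, so it fits as a step before the stop in 7.9 and does not permit rechallenge. The advice "In more severe cases treatment with corticosteroids should be considered" concerns treating the lung condition, not resuming AZD2014. The sequence is merely left unstated.
- **That 7.3.3 conflicts with 7.9.** It says "clinically significant abnormal ECG findings not present at pre dose should be reported as an AE" and "Further ECGs should be performed until recovery if a significant abnormality is detected", with no treatment action. It is an assessment section, and silence there is not a contradiction.
- **That 7.5.2.6 conflicts directly with 7.9.** It covers T-wave changes, which need not be clinically significant, so its trigger differs. It matters here only because the Table 2 footnote defers to it.

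**Conclusion.** The point holds for ECG changes: as written, Table 2 permits a restart that 7.9 forbids, and nothing resolves the difference. It is a minor consistency fix with a patient-safety rationale. The conflict is confined to first events that are expected to be manageable and settle within 14 days; in the other cases both sections end treatment.

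The conclusion rests on reading the stop in 7.9 as permanent, and on an ECG change judged clinically significant falling within the entry condition of Table 2. No effect on the response endpoint is claimed. The effect on tolerability is small, for the reason given in the working. For ILD the protocol needs a clarification, not a correction. The reference in 7.3.4 to a section 7.5.5, which does not exist, is clerical; the ILD text is 7.5.2.5.

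**What to change.** 1. In 7.5.1, state that the mandatory stops in 7.9 override Table 2 and all of 7.5.2.
2. In Table 2 and 7.5.2.6, state that ECG changes judged clinically significant lead to discontinuation under 7.9, and that other T-wave changes are monitored.
3. As a secondary clarification in 7.5.2.5: interrupt on suspicion, restart only if ILD and pneumonitis are excluded, and discontinue under 7.9 once ILD is confirmed. Section 7.1.2 already uses the suspend-and-exclude pattern for rituximab when progressive multifocal leukoencephalopathy is suspected.
4. In 7.3.4, correct the cross-reference from 7.5.5 to 7.5.2.5.

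The cost is a wording amendment. It needs no new visits, tests or data, and it leaves the sample size and decision rules unchanged.
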